8.3.4 TIME PERIOD AND FREQUENCY FOR EVENT ASSESSMENT AND FOLLOW-UP

The occurrence of an adverse event (AE) or serious adverse event (SAE) may come to the attention of study personnel during study visits and interviews of a study participant presenting for medical care, or upon review by a study monitor.

All AEs including local and systemic reactions not meeting the criteria for SAEs will be captured on the appropriate case report form (CRF). Information to be collected includes event description, time of onset, clinician's assessment of severity, relationship to study product (assessed only by those with the training and authority to make a diagnosis), and time of resolution/stabilization of the event. All AEs occurring while on study must be documented appropriately regardless of relationship. All AEs will be followed to adequate resolution.

Any medical condition that is present at the time that the participant is screened will be considered as baseline and not reported as an AE. However, if the study participant's condition deteriorates at any time during the study, it will be recorded as an AE.

Changes in the severity of an AE will be documented to allow an assessment of the duration of the event at each level of severity to be performed. AEs characterized as intermittent require documentation of onset and duration of each episode.

The investigator will record all reportable events with start dates occurring any time after informed consent is obtained until 7 days (for non-serious AEs) or 30 days (for SAEs) after the last day of study

participation. At each study visit, the investigator will inquire about the occurrence of AE/SAEs since the last visit. Events will be followed for outcome information until resolution or stabilization. If resolution has not occurred within 6 weeks after the study end date, the subject will be exited from the study, but must continue to be followed until the condition has resolved, returned to pre-study condition, or warrants no further follow-up.

8.3.5 ADVERSE EVENT (AE) REPORTING

Any AE observed by the investigator or reported by the subjects shall be documented on an Adverse Event Form. When an AE is initially discovered, the first page of the Adverse Event Form should be completed as well as the 'Treatment / Action' section. Care should be taken to describe the condition accurately.

8.3.6 SERIOUS ADVERSE EVENT REPORTING

The principal investigator at the site shall report all Serious Adverse Events to the Medical Monitor within 24 hours by phone or e-mail (see Section 10.1.5 for Medical Monitor contact information) and submit the Adverse Event Form to the reviewing Institutional Review Board (IRB) as soon as possible, but in no event later than 10 working days after the investigator first learns of the effect.

The study sponsor is responsible for conducting an evaluation of an SAE and shall report the results of such evaluation to the Food and Drug Administration (FDA) and to all reviewing IRBs and participating investigators within 10 working days after the sponsor first receives notice of the effect. Thereafter, the sponsor shall submit such additional reports concerning the effect as FDA requests.

[figure not shown]
8.3.7 DEVICE DEFICIENCIES

For the purpose of this protocol, device deficiencies are defined as any inadequacy of the study spectacles (i.e., spectacle lenses and spectacle frames) with respect to their identity, quality, durability, reliability, safety, or performance. For clarity, accidental damage should not be considered a device deficiency unless due to a quality issue.

All device deficiencies should be documented on the CRFs. The investigator should assess and document on the CRF whether the device deficiency would have led to a serious adverse event if:

- Suitable action had not been taken;
- Intervention had not been made; or
- Circumstances had been less fortunate.

9 STATISTICAL CONSIDERATIONS

[figure not shown]
9.1 STATISTICAL HYPOTHESES

The null and alternative primary hypotheses for this study are:

$$H_0: \mu_T - \mu_C \geq 0.03 \quad \text{versus} \quad H_A: \mu_T - \mu_C < 0.03$$

[figure not shown]
Here μ indicates the mean change in axial length between baseline and 6 months.

9.2 SAMPLE SIZE DETERMINATION

The study is sized to ensure an adequate power at an overall alpha level of 0.05 for treatment comparisons in axial length change from baseline at 6 months.

Assuming a drop-out rate of 10-20%, a study of 50-60 subjects achieves 80% power to detect non-inferiority

9.3 POPULATIONS FOR ANALYSES

The study data will be analyzed in one of the following analysis populations:

The **Per-Protocol (PP)** population will include all randomized subjects who follow the protocol without any major deviation(s) that could impact the integrity of the data. Reasons for exclusion from the PP population may include:

- use of the incorrect study spectacles
- poor compliance with the wearing regimen.

The **Safety** population will include all randomized subjects who use any of the study devices. Subjects will be grouped for analysis based on the actual device used.

9.4 STATISTICAL ANALYSES

9.4.1 GENERAL APPROACH

The analyses will be performed once all data have been entered into the EDC, cleaned and the database has been locked.

Descriptive summaries will include mean, standard deviation, median, and range for continuous variables and counts and percentages for categorical variables. Two-sided 95% confidence intervals (CIs) will be provided for the means and percentages. For key outcome measures, the difference between each of the test arms versus the control and the 95% CI of the difference will be computed.

All statistical analysis will be performed using SAS® (Version 9.4 or higher, SAS Institute Inc., Cary, NC, USA). Some graphical tools (such as EXCEL, PowerPoint) may be used to generate figures.

9.4.2 ANALYSIS OF THE STUDY CONDUCT

The number of subjects who are enrolled, discontinued (early discontinuation of treatment or early termination from the study), and complete the study (through 6 months after randomization) will be tabulated.

[figure not shown]
Reasons for early discontinuation of the treatment or early termination of from the study will be listed and summarized by treatment arm. Any eligibility criteria exceptions and other protocol deviations will also be summarized by treatment arm.

9.4.3 ANALYSIS OF TREATMENT COMPARABILITY

Demographic and baseline characteristics such as age, gender and race will be summarized for all randomized subjects. Other baseline characteristics such as baseline axial lengths and baseline SER will be summarized for all randomized subjects by treatment.

9.4.4 ANALYSIS OF THE PRIMARY EFFICACY ENDPOINTS

The main analysis of the primary efficacy outcome measures (i.e., change from baseline in axial length) will be on the PP population.

9.4.6 SAFETY ANALYSES

Adverse events will be tabulated by incidence overall, by device related, maximum severity, and those resulting in study discontinuation. Serious adverse events will be listed. Data summarized as well as additional collected data will be provided in supporting line listings. Ocular assessments such as BCVA, biomicroscopic slit lamp, ophthalmoscopy results and other findings will be summarized descriptively.

9.4.7 MISSING DATA

All possible efforts will be made to minimize missing data rate as missing data may potentially bias the outcome of the statistical analyses and the subsequent estimation of the magnitude of the treatment

effect. Due to having only one follow-up visit, it would not be appropriate to impute missing data. Therefore, the efficacy analysis will be completed on the PP population.

9.4.8 PLANNED INTERIM ANALYSES

There will be no interim analyses during this study.

10 SUPPORTING DOCUMENTATION AND OPERATIONAL CONSIDERATIONS

10.1 REGULATORY, ETHICAL, AND STUDY OVERSIGHT CONSIDERATIONS

10.1.1 INFORMED CONSENT PROCESS

10.1.1.1 CONSENT/ASSENT AND OTHER INFORMATIONAL DOCUMENTS PROVIDED TO PARTICIPANTS

Consent forms describing in detail the study, study interventions, study procedures, and risks are given to the participant and written documentation of informed consent is required prior to starting the study or dispensing study interventions.

For subjects who are 7 to 14 years of age, Assent forms will also be used to describe the study, study interventions, study procedures, and risks and written documentation of assent is required prior to starting study procedures or dispensing study interventions.

10.1.1.2 CONSENT PROCEDURES AND DOCUMENTATION

Informed consent (and assent) is a process that is initiated prior to the individual's agreeing to participate in the study and continues throughout the individual's study participation. Consent and Assent forms will be Institutional Review Board (IRB) approved and the participant and parent/guardian will be asked to read and review the document. The investigator will explain the research study to the participant and parent/guardian and answer any questions that may arise. A verbal explanation will be provided in terms suited to the participant's and parent/guardian's comprehension of the purposes, procedures, and potential risks of the study and of their rights as research participants. Participants and parent/guardian will have the opportunity to carefully review the written consent form and ask questions prior to signing. The participants and parent/guardian should have the opportunity to discuss the study with their family or surrogates or think about it prior to agreeing to participate. The

participant's parent will sign the informed consent document prior to any procedures being done specifically for the study. Participants and parent/guardian must be informed that participation is voluntary and that they may withdraw from the study at any time, without prejudice. A copy of the informed consent document (and assent document if applicable) will be given to the participants and parent/guardian for their records. The informed consent process will be conducted and documented in the source document (including the date) and the form shall be signed prior to the participant undergoing any study-specific procedure. The rights and welfare of the participants will be protected by emphasizing to them that the quality of their medical care will not be adversely affected if they decline to participate in this study.

10.1.2 STUDY DISCONTINUATION AND CLOSURE

This study may be temporarily suspended or prematurely terminated if there is sufficiently reasonable cause. Written notification, documenting the reason for study suspension or termination, will be provided by the study sponsor to the Principal Investigators. If the study is prematurely terminated or suspended, the Principal Investigator will promptly inform study participants, the Institutional Review Board (IRB) and will provide the reason(s) for the termination or suspension. Study participants will be contacted, as applicable, and be informed of changes to study visit schedule.

Circumstances that may warrant termination or suspension include, but are not limited to:

- Determination of unexpected, significant, or unacceptable risk to participants;
- Insufficient compliance to protocol requirements;
- Data that are not sufficiently complete and/or evaluable.

The study may resume once concerns about safety, protocol compliance, and data quality are addressed, and satisfy the sponsor, IRB, and/or Food and Drug Administration (FDA).

10.1.3 CONFIDENTIALITY AND PRIVACY

Participant confidentiality and privacy is strictly held in trust by the participating investigators, their staff, and the sponsor and their interventions. This confidentiality is extended to cover testing of biological samples and genetic tests in addition to the clinical information relating to participants. Therefore, the study protocol, documentation, data, and all other information generated will be held in strict confidence. No information concerning the study or the data will be released to any unauthorized third party without prior written approval of the sponsor.

All research activities will be conducted in as private a setting as possible.

The study monitor, other authorized representatives of the sponsor, representatives of the Institutional Review Board (IRB), or regulatory agencies may inspect all documents and records required to be maintained by the investigator, including but not limited to, the medical records for the participants in this study. The clinical study site will permit access to such records.

The study participant's contact information will be securely stored at each clinical site for internal use during the study. At the end of the study, all records will continue to be kept in a secure location for as long a period as dictated by the reviewing IRB, Institutional policies, or sponsor requirements.

10.1.5 CLINICAL MONITORING

Clinical site monitoring is conducted to ensure that the rights and well-being of trial participants are protected, that the reported trial data are accurate, complete, and verifiable, and that the conduct of the trial is in compliance with the currently approved protocol/amendment(s), ISO 14155:2011 - Clinical investigation of medical devices for human subjects -- Good clinical practice, and with applicable regulatory requirement(s).

Monitoring for this study will be performed by Visioncare Research, Limited following their written Standard Operating Procedures (SOPs). Both on-site and centralized monitoring methods may be used throughout the study as appropriate. A separate monitoring plan will be created for the study and will include more detailed about the following monitoring visits. Furthermore, audits may be conducted by the sponsor to ensure monitoring practices are performed consistently across all participating sites and that monitors are following the monitoring plan. The investigational site will provide direct access to all source data, documents, and reports for the purpose of monitoring and auditing by the CRO, sponsor, and inspection by regulatory authorities.

10.1.5.1 SITE QUALIFICATION VISIT

Qualified personnel or consultants of the sponsor (including the study monitor) will meet with investigators prior to the initiation of the study in order to review the adequacy of the potential subject population, facilities, and equipment with respect to the needs of the study and to familiarize the investigator with the study protocol.

10.1.5.2 SITE INITIATION VISIT

Qualified personnel or consultants of the sponsor (including the study monitor) will review the study procedures with the site before the initiation of subject enrolment to ensure all investigators and study staff are fully trained in ISO 14155:2011 GCP guidelines and the protocol.

10.1.5.3 INTERIM MONITORING VISITS AND CONSULTATION

Interim monitoring visits and telephone, fax, mail and/or email consultation will be performed during the course of the study to ensure the proper progress and documentation of the study findings. The schedule of monitoring visits will be based on the rate of enrolment and number of subjects enrolled at each site and shall ensure that the site is complying with ISO 14155:2011 GCP, that subjects are being properly selected, and that study data are being correctly recorded.

10.1.5.4 CLOSE-OUT MONITORING VISIT

Qualified personnel or consultants of the sponsor (including the study monitor) will visit the clinical site for formal close-out when all subjects have completed the final visit of the study to collect any outstanding forms and to ensure accountability of the study spectacles and all study supplies. An Investigator Study Completion Form will be completed by the investigator.

10.1.6 DATA COLLECTION, HANDLING, AND QUALITY ASSURANCE

Data collection is the responsibility of the clinical trial staff at the site under the supervision of the site investigator. The investigator is responsible for ensuring the accuracy, completeness, legibility, and timeliness of the data reported. All source documents should be completed in a neat, legible manner to ensure accurate interpretation of data. All of the data collection protocols will be standardized through study documentation, uniform study forms and uniform criteria for subject recruitment, including independent confirmation of eligibility by the CRO or Medical Monitor. Study personnel will be trained before collecting study data.

Clinical data, including adverse events (AEs), will be entered into Medrio, a 21 CFR Part 11-compliant data capture system provided by the CRO. The data system includes password protection and internal quality checks, such as automatic range checks, to identify data that appear inconsistent, incomplete, or inaccurate. Clinical data may be entered directly into electronic case report forms (eCRF), which may be then printed, verified and signed by the investigator and used as the source document.

The CRFs will be completed at the time of the visit. All clinical data generated in the study will be submitted to the CRO for quality assurance review and analysis. All forms will be reviewed for completeness and evident recording errors will be rectified by contacting the appropriate clinical site. Computerized editing routines will be used to identify missing, invalid, inconsistent, or questionable data entries for verification prior to data analysis. These data issues will be resolved by contacting the

relevant clinical site. All data files will be backed up routinely, with weekly backups stored at an alternative location.

10.1.6.1 STUDY RECORDS RETENTION

Study records must be retained until the later of: (i) a period of 2 years after the device clearance, or (ii) the period of time required under other Applicable Law. Thereafter, the Institution and Investigator will not destroy any such records unless they have obtained sponsor's prior written permission to do so and, at sponsor's request and expense, will transfer such records to sponsor rather than destroy them.

10.1.7 PROTOCOL DEVIATIONS

A protocol deviation is any noncompliance with the clinical trial protocol, ISO 14155:2011 - Clinical investigation of medical devices for human subjects -- Good clinical practice (GCP), or Manual of Procedures (MOP) requirements. The noncompliance may be either on the part of the subject, the investigator, or the study site staff. As a result of deviations, where appropriate and possible, corrective actions should be developed by the site and implemented promptly.

The site investigator should not make any changes to the study unless necessary to eliminate an apparent immediate hazard to subjects in the study. It is the responsibility of the site investigator to use continuous vigilance to identify and report deviations within 24 hours of identification of the protocol deviation to the CRO and sponsor and within 10 working days to the IRB or otherwise per their policies. The site investigator is responsible for knowing and adhering to the reviewing IRB requirements.

10.2 PUBLICATION POLICY

The sponsor and its designees will have the right to publish or otherwise publicly disclose the information contained in or related to the study in any form without the written consent of the investigators.

[figure not shown]
At any time following the first publication of the study results from all clinical study sites participating in the study, the investigators may have the right to independently publish or present their portion of the study results after proper review by the sponsor. Investigators should refer to their Clinical Trial Agreement for more detailed information.

10.3 ABBREVIATIONS (TABLE 7)

AE	Adverse Event
AL	Axial Length
BCVA	Best-corrected Visual Acuity
CFR	Code of Federal Regulations
CI	Confidence Interval
cm	Centimeter
CRO	Clinical Research Organization
CRF	Case Report Form
D	Diopter(s)
DC	Diopter(s) Cylinder
DOT	Diffusion Optics Technology
EDC	Electronic Data Capture
eCRF	Electronic Case Report Forms
FDA	Food and Drug Administration
GCP	Good Clinical Practice
HIPAA	Health Insurance Portability and Accountability Act
IB	Investigator’s Brochure
IDE	Investigational Device Exemption
IRB	Institutional Review Board
ISO	International Organization for Standardization
logMAR	Log of Minimum Angle of Resolution
mm	Millimeter
MOP	Manual of Procedures
NIH	National Institutes of Health
OC	Optical Center
OD	Oculus Dexter (right eye)
OS	Oculus Sinister (left eye)
PD	Pupillary Distance
PI	Principal Investigator
QA	Quality Assurance
SAE	Serious Adverse Event
SER	Spherical Equivalent Refraction
SOA	Schedule of Activities
SOP	Standard Operating Procedure
µm	Micron
UP	Unanticipated Problem
US	United States
VA	Visual Acuity

10.4 PROTOCOL AMENDMENT HISTORY

TABLE 8 below is intended to capture changes of IRB-approved versions of the protocol, including a description of the change and rationale. A Summary of Changes table for the current amendment is located in the Protocol Title Page.

Version	Date	Description of Change	Brief Rationale
1.0	04 OCT 2019	Original Version	N/A
1.1	05 AUG 2020	
 • Date and version number updated throughout document • Reference (#26) in Section 8.2 was added for parent questionnaire  
 • Title of Section 9.4.3 corrected to remove the word "arm" 	
 • Version control • Missing bookmark • Typographical error correction

1. STATISTICAL HYPOTHESES

The null and alternative hypotheses for this study are: The null and alternative primary hypotheses for this study are:

$$H_0: \mu_t - \mu_c \geq 0.03 \quad \text{versus} \quad H_a: \mu_t - \mu_c < 0.03$$

Here μ indicates the mean change in axial length between baseline and 6 months.

2. SAMPLE SIZE DETERMINATION

The study is sized to ensure an adequate power at an overall alpha level of 0.05 for treatment comparisons in axial length change from baseline at 6 months. Assuming axial length change from baseline has a standard deviation (SD) of approximately 0.31 mm at 12 months²⁸. Therefore, it can be assumed that the SD at 6 months (SD_{6m}) is ≤ 0.31 mm. It has also been assumed that there will be no difference in mean AL change between the test and control lens types.

Power	80%
SD at 6m (each eye)	0.095
Between-eye correlation	0.85
SD of DDAL	0.053
True Difference in DDAL	0.00 mm
Equivalent/NI Margin	0.03 mm

Assuming a drop-out rate of 10-20%, a study of 50-60 subjects achieves 98% power to detect non-inferiority using a one-sided t-test when the margin of non-inferiority is 0.03 mm and the true difference between the treatments is 0.00 mm. The data are drawn from a single population with a standard deviation of 0.053 and the significance level (alpha) of the test is 0.050.

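### Does the 98% power in SAP Section 2 fail because the cited SD of 0.31 mm does not lead to the 0.095 mm used?

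*SAP*

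**What the plan says.** SAP Section 2 cites one external variability figure, that "axial length change from baseline has a standard deviation (SD) of approximately 0.31 mm at 12 months", and infers only an upper bound: the SD at 6 months is at most 0.31 mm. The input table then gives "SD at 6m (each eye) 0.095" and "Between-eye correlation 0.85", an SD of 0.053 mm for the between-eye difference (labelled DDAL), a true difference of zero and a margin of 0.03 mm. The power statement is "Assuming a drop-out rate of 10-20%, a study of 50-60 subjects achieves 98% power to detect non-inferiority", with "a standard deviation of 0.053 and the significance level (alpha) of the test is 0.050". The test is one-sided.

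The design is contralateral (Protocol 6.3): each child wears the test lens on one eye and the control lens on the other. SAP 4.4 judges non-inferiority by whether the upper limit of the 95% confidence interval for the difference lies below 0.03 mm.

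**The concern.** The wording reads as if the planning SD came from the cited study, but an upper bound of 0.31 mm does not produce 0.095 mm, which is 31% of it (0.095 / 0.31 = 0.306). No scaling step is shown, and the correlation of 0.85 has no visible source either. Simple ways of taking a 12-month SD to 6 months give larger values: 0.31 / 2 = 0.155 mm if the SD grows in proportion to time, or 0.31 / √2 = 0.219 mm if the variance does. If the true variability were that large and the correlation stayed at 0.85, the trial would have well under 98% power. A comparison of two truly equivalent lenses could then end inconclusively more often than the SAP suggests.

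**Working it through.** **Inputs from SAP Section 2.** Margin 0.03 mm; true difference 0; per-eye SD 0.095 mm; correlation 0.85; SD of the difference 0.053 mm; one-sided alpha 0.05; 50-60 children with 10-20% drop-out. Evaluable children run from 50 × 0.80 = 40 to 60 × 0.90 = 54.

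**Formulas.** SD of the difference = SD(eye) × √(2(1 − ρ)). Power of the one-sample t-test on the differences = 1 − F(t(1−α, n−1); n−1, δ), where F is the noncentral t distribution function and δ = 0.03 × √n / SD of the difference.

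**Step 1: the SD of the difference.** 0.095 × √(2 × 0.15) = 0.095 × √0.30 = 0.0520 mm, close to the stated 0.053. The stated value would need a per-eye SD of 0.0968 mm; the gap is immaterial.

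**Step 2: the stated power.** With 0.053 mm and one-sided 0.05:

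| Evaluable n | δ | Power |
|---|---|---|
| 40 | 3.58 | 96.9% |
| 45 | 3.80 | 98.2% |
| 48 | 3.92 | 98.7% |
| 54 | 4.16 | 99.3% |

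The 98% reproduces.

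**Step 3: larger per-eye SD, correlation held at 0.85.** The first two SDs rest on time-scaling rules assumed here, since the documents give none. The third is the SAP's own bound.

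| Per-eye SD (mm) | SD of difference (mm) | Power, n = 40-54, one-sided 0.05 |
|---|---|---|
| 0.155 | 0.0849 | 71-82% |
| 0.219 | 0.120 | 46-57% |
| 0.31 | 0.170 | 29-36% |

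If the 95% interval in SAP 4.4 is read as two-sided, the test is at one-sided 0.025. The first row then becomes 59-72%, but that changes alpha as well as the SD. The SAP's own 0.053 mm gives 93.7-98.3% at 0.025. The difference between the two alphas is a separate matter and says nothing about the choice of SD.

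**Step 4: larger per-eye SD, correlation allowed to move.** Variation between children that both eyes share cancels in the difference. If the extra variability in 0.155 mm over 0.095 mm is of that kind, the eye-specific variance stays at 0.095² × 0.15 = 0.001354. The matching correlation is 1 − 0.001354 / 0.155² = 1 − 0.001354 / 0.024025 = 0.944, and the SD of the difference is √(2 × 0.001354) = 0.052 mm, as in Step 1. At a per-eye SD of 0.155 mm:

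| Correlation | SD of difference (mm) | Power, n = 40-54, one-sided 0.05 |
|---|---|---|
| 0.85 | 0.0849 | 71-82% |
| 0.90 | 0.0693 | 85-93% |
| 0.944 | 0.052 | 97-99% |

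**Step 5: room for error.** Power at one-sided 0.05 stays at 80% or more while the SD of the difference is no larger than 0.075 mm (n = 40) to 0.0875 mm (n = 54). That is 0.075 / 0.053 = 1.4 to 0.0875 / 0.053 = 1.65 times the planning value.

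**The case for a change.** The strongest case for a change is that the SAP's written reasoning goes from 0.31 mm to an inequality and stops, after which two unsupported inputs carry the whole power claim. Power here is fixed by n, alpha and the SD of the difference, so an unsupported SD means an unsupported 98%. The correlation could also be lower than assumed: keeping 0.095 mm but taking 0.70 gives an SD of the difference of 0.0736 mm and power of 81-91% at one-sided 0.05. A sentence of justification or a short sensitivity table would be cheap, and readers of an inconclusive trial would want to know whether 98% had been a credible expectation.

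The factual part stands: the visible text gives no basis for 0.095 or 0.85, and the 98% is conditional on them. It does not follow that the cited study contradicts the planning values. The SAP takes only a bound from that study, and 0.095 mm meets it. A per-eye SD alone cannot settle the power of a paired-eye comparison (Step 4). A sensitivity table would need ranges for SD and correlation that the documents do not supply. Protocol 9.1.1, on the margin, is listed in the contents but absent from the public text, and other parts are redacted, so a basis may exist that cannot be seen here.

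**Conclusion.** No change to the plan is needed. The 98% is arithmetically right for an SD of the between-eye difference of 0.053 mm at one-sided 0.05 (96.9-99.3% over 40-54 evaluable children). The documents neither establish that SD nor contradict it. If half the cited SD applied at 6 months, power at the same alpha would lie anywhere from 71-82% (correlation 0.85) to 97-99% (correlation about 0.944), depending on how much of the variation the two eyes share. Both the halving and those correlations are assumptions.

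An optimistic planning SD would not bias the estimated difference or raise the type I error. The interval in SAP 4.4 uses the variability actually observed, so any shortfall would appear as a wider interval and a greater chance of an inconclusive result. Writing down the source of 0.095 and 0.85 would make the section easier to follow, but with no change in enrolment, analysis or decision rule in question it would leave every result and conclusion as it is.

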4.4 ANALYSIS OF THE PRIMARY EFFICACY ENDPOINTS

The main analysis of the primary efficacy outcome measures (i.e., change from baseline in axial length) will be on the PP population.

A mixed effect model including the following terms will be used to analyze the difference in change in axial length between treatments: treatment, order, age, gender, and treatment-by-order interaction as factors, and the baseline axial length as a covariate. Estimates for the mean change from baseline at 6 months will be calculated from the model [i.e., least-squared (LS) means]. The standard error and 95% confidence interval (CI) of the LS mean will be provided. The difference in LS mean change from baseline between the test and the control lens and the corresponding 95% CI will be derived from the model. If the upper limit of the CI is less than the non-inferiority bound of 0.03 mm, then the hypothesis of the test lens being non-inferior to the control lens will be met. Also, the p-values for testing the pairwise differences in LS means against a zero value will be computed based on t-tests.

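### The protocol and the SAP state different power, 80% and 98%, for the same 50-60 subjects and the same drop-out; the SAP's inputs support about 98%

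*SAP*

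**What the plan says.** Protocol Section 9.2: "Assuming a drop-out rate of 10-20%, a study of 50-60 subjects achieves 80% power to detect non-inferiority". The visible sentence ends there. The alpha is given just before it: "The study is sized to ensure an adequate power at an overall alpha level of 0.05". No SD, assumed true difference or sidedness is visible.

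SAP Section 2, with the same 10-20% drop-out and a one-sided t-test: "a study of 50-60 subjects achieves 98% power to detect non-inferiority". The SAP goes on to give the margin (0.03 mm), the true difference (0.00 mm) and the remaining inputs: "The data are drawn from a single population with a standard deviation of 0.053" and "the significance level (alpha) of the test is 0.050". Its table lists a per-eye SD at 6 months of 0.095, a between-eye correlation of 0.85 and an SD of the difference of 0.053. The table also has a row setting power at 80%, with no sample size attached.

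Both documents state the same hypotheses with the same 0.03 bound (Protocol 9.1, SAP Section 1). For the decision, SAP Section 4.4 derives a 95% confidence interval from the model, and non-inferiority is met "If the upper limit of the CI is less than the non-inferiority bound of 0.03 mm".

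**The concern.** Both documents present their figure as the power the study achieves, for the same number of subjects, drop-out, endpoint, margin and overall alpha. On one set of inputs, both cannot be right. The SAP also carries both numbers, 80% in its table and 98% in its text, without saying how they relate.

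What is at stake is the basis of the sample size. At 98%, the planned size is well above what 80% power requires. At 80%, it would be just sufficient, and the assumptions behind it must be less favourable than those in the SAP table. A reader cannot tell which of these was intended.

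**Working it through.** **Inputs** (SAP Section 2): margin 0.03 mm, true difference 0, SD of the between-eye difference 0.053 mm, one-sided alpha 0.05. Each child wears the test lens on one eye and the control lens on the other (Protocol 6.3), so the test is a paired, one-sample t-test.

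**Evaluable children.** 50 × 0.80 = 40 at the low end and 60 × 0.90 = 54 at the high end. Between them, 50 × 0.90 = 45 and 60 × 0.80 = 48.

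**SD check.** 0.095 × √(2 × (1 − 0.85)) = 0.095 × √0.30 = 0.0520, against 0.053 stated. The difference is small; using 0.0520 gives 97.4% to 99.4% over the same range.

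**Power.** Exact noncentral t with n − 1 degrees of freedom and noncentrality 0.03 / (0.053/√n). At n = 45 the noncentrality is 0.03 × 6.708 / 0.053 = 3.80 and the critical value is 1.680, giving 98.2%. This reproduces the SAP's 98%; 45 is the smallest n that reaches it.

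| Evaluable n | One-sided 0.05 | One-sided 0.025 |
|---|---|---|
| 21 | 80.5% | 69.4% |
| 27 | 88.8% | 80.8% |
| 40 | 96.9% | 93.7% |
| 45 | 98.2% | 96.0% |
| 48 | 98.7% | 97.0% |
| 54 | 99.3% | 98.3% |

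The last column applies if the 95% interval in SAP 4.4 is two-sided, since its upper limit then tests at one-sided 0.025. That lowers power by 1 to 3 points over 40-54 and does not bring it near 80%.

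**Where 80% arises.** With the SAP inputs, 80% is first reached at 21 evaluable children (27 at one-sided 0.025). Allowing for 10-20% drop-out, 21 evaluable means 24 to 27 enrolled (21/0.90 = 23.3; 21/0.80 = 26.25), about half the planned number.

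**What would make 80% true at 40-54 evaluable**, one-sided 0.05, changing one input at a time:

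- SD of the difference of 0.0750 mm (n = 40) to 0.0875 mm (n = 54), instead of 0.053. With the per-eye SD kept at 0.095, the correlation would be 1 − 0.0750²/(2 × 0.095²) = 0.69 to 1 − 0.0875²/(2 × 0.095²) = 0.58. With the correlation kept at 0.85, the per-eye SD would be 0.0750/√0.30 = 0.137 to 0.0875/√0.30 = 0.160.
- Or a true difference of 0.009 mm (n = 40) to 0.012 mm (n = 54), instead of 0.

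**The case against.** The strongest reply is that the protocol's inputs were probably removed from the public copy. Its sentence stops mid-statement where the SAP's continues, and Section 9.1.1 on the margin is in the contents list but not in the visible body. The missing explanation may therefore be an effect of redaction, and the 80% may be sound on other inputs. The SAP leaves room for this: it supports its SD only by 0.31 mm at 12 months and an upper bound of 0.31 mm at 6 months, and the step to 0.095 is not shown. As an illustration only, if the 6-month per-eye SD were half of 0.31 (0.155, an assumption not in the documents), the SD of the difference at correlation 0.85 would be 0.155 × √0.30 = 0.085. Power would then be 71% to 82% over 40-54 evaluable. This stands as a limit on the cause: the protocol's 80% cannot be called a miscalculation. It does not remove the conflict, because the two documents would then rest on different assumptions for one trial.

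A second reply is that 80% is the design target and 98% the achieved value, and that a trial with 98% power meets an 80% requirement. This is plausible for the SAP table row. It does not fit the protocol sentence, which says the study achieves 80% and mentions neither a target nor a minimum. A label would settle it.

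A third reply is that nothing in the conduct, analysis or conclusion depends on the printed figure. That is correct, and it limits the severity.

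**Conclusion.** The concern holds. The two documents give power figures 18 points apart for the same subjects and drop-out. The SAP's 98% reproduces from its own inputs; 80% does not at any evaluable number from 40 to 54. Either the protocol figure is wrong as a statement of achieved power, or it rests on inputs that differ from those in the SAP.

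This rests on the paired design, the SD of 0.053 mm and a true difference of 0, all as stated in the SAP. On those terms power is at least 93.7% under either alpha, so this is a reporting inconsistency and not evidence of an underpowered trial. That reassurance is only as good as the 0.053. The existence of the conflict is certain; its cause is not. It should be fixed, because stated power is a figure the design relies on.

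**What to change.** 1. Confirm what the protocol's 80% was based on.
2. If it rests on the SAP's inputs, state one achieved power in Protocol 9.2 and SAP Section 2, with the evaluable number (40-54) beside it: about 97-99% at one-sided 0.05, or about 94-98% if the two-sided 95% interval in SAP 4.4 governs.
3. If it rests on a larger SD or a non-zero true difference, put that value in the SAP table and restate the 98% accordingly.
4. Label the 80% row in the SAP table as the design target, or delete it.

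The cost is a wording correction in both documents. Sample size, margin, analysis and decision rule stay as they are.
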